8 STUDY OBJECTIVES

The primary objectives of the study are:

- To assess the safety of a single intravenous administration of a recombinant AAV5 encoding human coagulation FVIII (AAV5-hFVIII-SQ) vector.
- To determine the dose of AAV5-hFVIII-SQ required to achieve expression of hFVIII at or above 5% of normal activity (≥5 IU/dL) at 16 weeks after infusion. The kinetics, duration and magnitude of AAV-mediated hFVIII activity in individuals with haemophilia A will be determined and correlated to an appropriate BMN 270 dose.

The secondary objectives of the study are:

- To describe the immune response to the hFVIII transgene product and AAV capsid proteins following systemic administration of AAV5-hFVIII-SQ
- To assess the impact of BMN 270 on the frequency of FVIII replacement therapy during the study
- To assess the impact of BMN 270 on the number of bleeding episodes requiring treatment during the study

The exploratory objectives of the liver biopsy substudy are:

- To examine the histopathology of the liver following BMN 270 therapy, including assessing for possible safety findings (eg, fibrosis, fatty liver disease, lymphocytic invasion)
- To quantify FVIII DNA, RNA, and protein expression within hepatocytes
- To determine which forms of rAAV genomic DNA (eg, concatemers) are present at the time of biopsy
- To determine the transduction pattern in humans (ie, peri-portal hepatocytes, central vein hepatocytes)

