- ^e Sample testing during Safety Follow-Up is not required if at least 3 consecutive samples are cleared during the Post-Infusion Follow-Up period. Subjects who have not had 3 consecutive negative samples by Week 52 should continue to have PCR testing every 4 weeks (during Year 2) or every 6 weeks (during Years 3-5) until 3 consecutive negative samples are documented (or upon consultation between the Investigator and Medical Monitor).
- ^fHaemo-QoL-A QoL assessment during Years 2-5 of Safety Follow-up should be performed at the second Q12W visit each year and at every End of Year visit.
- ^g Blood samples will be collected to evaluate biochemical, molecular, cellular, and genetic/genomic aspects relevant to hemophilia A, coagulation, and/or AAV gene transfer, and to develop assays used for these evaluations. Subjects may choose to opt out of the exploratory genetic/genomic research being done to study or try to discover genes that are not yet known to be associated with hemophilia A. While exploratory samples will be collected at the time points indicated above, testing of these samples (including any other exploratory assessments) will be performed only as deemed necessary by the Sponsor.
- ^h Subjects who meet the definition of treatment failure to BMN 270 therapy after Week 52 may omit the Q4W and Q6W visits during Years 2-5, and must attend only the Q12W and End of Year visits. Such subjects following the abbreviated schedule who have not yet cleared vector shedding in all fluids must still provide samples Q4W (during Year 2) or Q6W (during Years 3-5) until vector shedding has been cleared (but do not need to do other scheduled assessments at those visit dates).

270-201 Amendment 8

					Steroid T	reatment	Period ^d					Post-Steroid Period ^c					
	Week 1	Week 2	Week 3	Week 4	Week 5	Week 6	Week 7	Week 8	Week 9	Week 10	Week 11 ^b	Week 1	Week 2	Week 3	Week 4	Week 13	
Therapeutic corticosteroids (dose in mg/day) ^a	60 mg	60 mg	40 mg	40 mg	30 mg	30 mg	20 mg	20 mg	15 mg	10 mg	5 mg						
FVIII activity testing												Х	Х	Х	Х		
Liver testing												Х	Х	Х	Х		
Hepatitis B testing ^e						Х						Х				Х	
HCV Viral Load ^e						Х						Х				Х	

Table 9.1.6: Schedule of Events – Therapeutic Corticosteroids for LT Elevations

^a Therapeutic corticosteroids may be initiated when a subject's ALT value is ≥ 1.5x ULN or based on review of FVIII and liver enzyme data after consultation between the Investigator and the Medical Monitor.

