12.8 Safety Follow-Up – Years 2-5

Subjects who do not respond to BMN 270 treatment (ie, treatment failure, manifesting as either failure to achieve FVIII activity ≥ 5 IU/dL by Week 52 or inability to maintain independence from prophylactic FVIII replacement therapy due to joint bleeding episodes, in the judgment of the Investigator) may, at the Investigator's discretion and after discussion with the Medical Monitor, follow an abbreviated visit schedule after Week 52 of the study by attending only the Q12W and End of Year visits during Years 2-5.

Subjects who meet the definition of treatment failure and wish to follow an abbreviated schedule but who have not cleared vector shedding from all fluids must still provide samples for assessment every 4 weeks (during Year 2) or every 6 weeks (during Years 3-5) until vector shedding has cleared (but do not have to perform other scheduled assessments at those study visits).

During Years 2-5 of Safety Follow-up, the following procedures will be completed:

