12.8.1 Year 2 – Every 4 Weeks (not required for treatment failure)

During Year 2, every 4 weeks (\pm 2 weeks), the following procedures will be performed:

- Assessment of Adverse Events and Concomitant Medications (including review of subject diary for bleeding and FVIII use)
- Liver Tests (refer to Table 9.7.8.3.1) local laboratory assessment
 - LTs may be monitored more or less frequently (and in particular when ALT values are >1.5x ULN) based on discussion between the Medical Monitor and the Investigator and review of subject data.
- FVIII activity level local laboratory assessment
 - FVIII activity level (one-stage clotting assay)
 - FVIII activity level (chromogenic substrate assay)

- Liver Tests (refer to Table 9.7.8.3.1) central laboratory assessment
 - LTs may be monitored more or less frequently (and in particular when ALT values are >1.5x ULN) based on discussion between the Medical Monitor and the Investigator and review of subject data.
- FVIII Assays central laboratory assessment
 - FVIII activity level (one-stage clotting assay)
 - FVIII activity level (chromogenic substrate assay)
 - FVIII coagulation activity exploratory assay
 - o Bethesda assay (with Nijmegen modification) for FVIII inhibitor level
 - FVIII antigen (ELISA)

Note: If a subject has used FVIII within 72 hours of a measurement day, all efforts should be made to obtain FVIII activity measurements when a 72-hour interval without FVIII use is achieved; the 72-hour wash-out period is only intended for subjects who have achieved FVIII \geq 5 IU/dL at 16 weeks after BMN 270 infusion and who have not resumed standard of care FVIII replacement therapy.

- PCR of vector DNA in blood, saliva, urine, semen, and stools (if required)
 - Sample testing during Year 2 is not required if at least 3 consecutive samples are negative during the Post-Infusion Follow-Up period in Weeks 1-52.
 Subjects who have not had 3 consecutive negative semen samples by Week 52 should continue to have PCR testing of semen every 4 weeks during Year 2 until 3 consecutive negative samples are documented (or upon consultation between the Investigator and Medical Monitor).

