12.8.2 Years 3-5 – Every 6 Weeks (not required for treatment failure)

During Years 3-5, every 6 weeks (± 2 weeks), the following procedures will be performed:

- Assessment of Adverse Events and Concomitant Medications (including review of subject diary for bleeding and FVIII use)
- Liver Tests (refer to Table 9.7.8.3.1) local laboratory assessment

- LTs may be monitored more or less frequently (and in particular when ALT values are >1.5x ULN) based on discussion between the Medical Monitor and the Investigator and review of subject data.
- FVIII activity level local laboratory assessment
 - FVIII activity level (one-stage clotting assay)
 - FVIII activity level (chromogenic substrate assay)
- Liver Tests (refer to Table 9.7.8.3.1) central laboratory assessment
 - LTs may be monitored more or less frequently (and in particular when ALT values are >1.5x ULN) based on discussion between the Medical Monitor and the Investigator and review of subject data.
- FVIII Assays central laboratory assessment
 - FVIII activity level (one-stage clotting assay)
 - FVIII activity level (chromogenic substrate assay)
 - FVIII coagulation activity exploratory assay
 - Bethesda assay (with Nijmegen modification) for FVIII inhibitor level
 - FVIII antigen (ELISA)

Note: If a subject has used FVIII within 72 hours of a measurement day, all efforts should be made to obtain FVIII activity measurements when a 72-hour interval without FVIII use is achieved; the 72-hour wash-out period is only intended for subjects who have achieved FVIII \geq 5 IU/dL at 16 weeks after BMN 270 infusion and who have not resumed standard of care FVIII replacement therapy.

- PCR of vector DNA in blood, saliva, urine, semen, and stools (if required)
 - Sample testing during Years 3-5 is not required if at least 3 consecutive samples are negative during the Post-Infusion Follow-Up period in Weeks 1-52 and/or Year 2. Subjects who have not had 3 consecutive negative semen samples by Week 52 should continue to have PCR testing of semen every 6 weeks during Years 3-5 until 3 consecutive negative samples are documented (or upon consultation between the Investigator and Medical Monitor).

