14.1.2 Procedures for Accounting for Missing, Unused and Spurious Data

Missing data will not be imputed.

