14.2 Primary and Secondary Efficacy Analysis

The subjects will be followed in a longitudinal manner and all the relevant information will be collected. The analysis of the data will be descriptive in nature. Descriptive statistics include the number of subjects, mean, median, standard deviation, minimum, and maximum for continuous variables and count and percent for categorical variables. Efficacy variables will be summarized by dose cohort at each time point. Relationship between dose and efficacy results will be examined.

Data collected in a longitudinal manner may be analyzed using longitudinal methods such as mixed effect model which takes into account the correlation among the observation taken at various time points within a participant. Efficacy is a secondary endpoint, defined as biologically active hFVIII at ≥ 5 IU/dL by chromogenic substrate assay and/or one-stage clotting assay as measured by the central laboratory at 16 weeks following study treatment. hFVIII activity will be assessed weekly during the study period. We can only assess the true steady state of hFVIII protein produced from BMN 270 after a minimum of 72 hours has elapsed since the last infusion of FVIII protein concentrates.

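### At up to 24 of the 40 scheduled Year 2-5 FVIII visits, cohort summaries may leave out treatment failures because of their outcome

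*Protocol*

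**What the plan says.** The text used is Amendment 8.

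- **Objective.** Section 8 attaches long-term expression to a primary objective: "The kinetics, duration and magnitude of AAV-mediated hFVIII activity in individuals with haemophilia A will be determined".
- **Who counts as a failure.** Section 12.8 gives two routes. One is not reaching 5 IU/dL by Week 52. The other is "inability to maintain independence from prophylactic FVIII replacement therapy due to joint bleeding episodes, in the judgment of the Investigator".
- **What a failure may do.** Such a subject may, "at the Investigator's discretion and after discussion with the Medical Monitor, follow an abbreviated visit schedule after Week 52 of the study". Table 9.1.5, footnote h, says these subjects "may omit the Q4W and Q6W visits during Years 2-5, and must attend only the Q12W and End of Year visits". The headings of Sections 12.8.1 and 12.8.2, which list the Q4W and Q6W procedures including the central FVIII assays, mark those visits as not required for treatment failure.
- **What everyone must do.** Section 12.8.3 requires central FVIII assays of all subjects at 16 named visits, four in each of Years 2 to 5, the last of each year being the End of Year visit.
- **How the data are summarised.** Section 14.2: "Efficacy variables will be summarized by dose cohort at each time point". Section 14.1.2: "Missing data will not be imputed". A mixed effect model is permitted in Section 14.2 but not required.

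**The concern.** Whether a subject is present at a Q4W or Q6W visit can depend on whether treatment worked. Under the stated rules, a cohort summary at such a visit uses whoever was measured. Failures who took the shorter schedule drop out of both numerator and denominator, then return at the next Q12W or End of Year visit. The plotted cohort curve could rise and fall with no change in any subject's expression, and the skipped visits would generally read too high.

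The cohorts are very small: up to four subjects in each of Cohorts 1-3 and three plus three in Cohort 4 (Section 9.1), subject to reallocation by the Data Review Board. One absent subject can move a mean noticeably. What is at stake is the description of duration and magnitude of expression, and any long-term percentage at or above 5 IU/dL.

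**Working it through.** The protocol gives no count of affected visits, so there is no figure of its own to reproduce. The count below is by enumeration.

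**Inputs**
- Year 2 interval of 4 weeks (Section 12.8.1).
- Years 3-5 interval of 6 weeks (Section 12.8.2), restarting after each End of Year visit (Table 9.1.5, first note).
- Visits required of all (Section 12.8.3): Weeks 64, 76, 88, 104; 116, 128, 140, 156; 168, 180, 192, 208; 220, 232, 244, 260.

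**Year 2**
- Weeks 56 to 104 in steps of 4: (104 − 56)/4 + 1 = 13 visits.
- Four are required of all, so 13 − 4 = 9 may be skipped.

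**Years 3, 4 and 5 (Year 3 shown)**
- Q6W visits: Weeks 110, 116, 122, 128, 134, 140, 146, 152, which is 8. Adding Week 156 gives 9.
- Four are required of all, so 9 − 4 = 5 may be skipped: Weeks 110, 122, 134, 146 and 152.

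**Total**
- Visits: 13 + 3 × 9 = 40.
- Skippable: 9 + 3 × 5 = 24, or 24/40 = 60%.
- Kept by all: 40 − 24 = 16.

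**Sensitivity of the count**
- If the last Q6W visit of each of Years 3-5, four weeks before the End of Year visit, is not held: 21 of 37.
- If failure is declared only after Week 104: 15 of 40 (38%). After Week 156: 10 of 40 (25%). After Week 208: 5 of 40 (12.5%).

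**Size of the distortion (assumed values; the protocol gives none)**

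With n subjects, f of them absent failures at level F and the rest at level R, the all-subject mean is [(n − f)R + fF]/n, while the observed mean is R.

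- n = 6, f = 1, R = 50, F = 2 IU/dL: (5 × 50 + 2)/6 = 42.0. The summary would show 50, and 50/42 − 1 = 19% too high. The percentage at or above 5 IU/dL would be 5/6 = 83% with everyone present and 100% as observed.
- n = 6, f = 2, same levels: (4 × 50 + 2 × 2)/6 = 34.0, and 50/34 − 1 = 47% too high.
- Range over cohort sizes 4, 6 and 7, R of 20 or 50 and F of 1 or 4 IU/dL: 13-32% too high with one absent failure, 30-96% with two.

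**After the fix.** With summaries restricted to the 16 common visits, none of the 16 has absences of failures caused by the abbreviated schedule.

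**The case against.** **The worst case is not a fact.** A reader might infer that most long-term cohort means describe responders only. The documents do not support that. The shorter schedule is discretionary, and no number of failures or users is given. Reaching 60% needs the failures in a cohort to be on the shorter schedule from Week 52. Cohorts 1 and 2 may hold a single subject; if that subject fails and skips a visit, there is no mean at all rather than a responder mean. This objection stands and limits the claim to what may happen.

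**Failures stay measured and the main result is safe.** They are assayed at 16 visits, including every End of Year visit, and efficacy at Week 16 is settled before any abbreviated visit. No test or decision rule depends on the later summaries. This stands, and lowers the priority.

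**Choice of display visits belongs to the SAP.** Section 14.1 leaves detail to the SAP and Section 14.9 lets it prevail; it is not available here. This stands only in part. The protocol itself fixes both the by-time-point summary and the rule of no imputation, and its visit schedule conflicts with them.

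**A mixed model is allowed.** For failures defined by measured FVIII, later absence depends on values already observed, which such a model can accommodate. But the model is optional while the descriptive summary is mandatory.

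**Thinning is not confined to failures.** Table 9.1.5, footnotes c and d, allow FVIII sampling to be adjusted when levels are elevated or stable, so other subjects may be absent too. This stands and is a further reason to show who contributes at each visit.

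**Counting every failure as below 5 IU/dL would be wrong.** It is a tempting remedy, but the bleeding and prophylaxis route can include a subject whose measured FVIII is 5 IU/dL or more. This stands.

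**Conclusion.** The point holds in limited form. At up to 24 of 40 Year 2-5 FVIII visits, the stated rules allow cohort means and percentages at or above 5 IU/dL to exclude treatment failures because of their outcome, with an expected upward bias and denominators that shift between adjacent visits. The count is exact given the schedule, but it is a maximum. The percentage distortions rest on assumed FVIII levels and numbers of failures.

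The upward direction is clear for failures with low measured FVIII. It is less certain for those who fail on the bleeding route. The 72-hour wash-out is not intended for subjects who have resumed standard replacement therapy (Section 9.7.2), so their values at the 16 common visits may include exogenous FVIII. Those visits are a better basis for summary, not a perfectly clean one.

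Section 7.3.1 reports second-year mean activity above 50 IU/dL. A reader might suspect that this statement is a product of skipped visits; nothing in the protocol connects the two. The Week 16 endpoint is unaffected. This is a cheap improvement, not a must-fix.

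**What to change.** In Section 14.2, state that cohort summaries after Week 52 and the main longitudinal plot use the 16 Q12W and End of Year visits required of all subjects: Weeks 64, 76, 88, 104, 116, 128, 140, 156, 168, 180, 192, 208, 220, 232, 244 and 260. In addition:

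- Show n and the number of treatment failures at each of these visits.
- Flag values taken within 72 hours of exogenous FVIII or after replacement therapy was resumed.
- Use the remaining Q4W and Q6W values in individual profiles only.
- Present any summary that counts treatment failures as non-responders as a separately labelled composite that does not override measured FVIII.

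No visit, assay or clinical rule changes. The cost is a short addition to the text and fewer plotted cohort means.

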Because subjects develop neutralizing immunity upon exposure to the capsid, re-challenge of vector is not a likely treatment option and these subjects have effectively a single opportunity for therapy using this AAV capsid. Efficacy will be determined by FVIII activity at 16 weeks post dose. Safety will be evaluated for approximately 5 years after dosing. Any safety signal may trigger a review of the data and possible additional immunogenicity studies that include an assessment of cellular immune responses using collected PBMC. Additionally, if any of the events listed in Section 9.3.4.1 occur, enrollment into the trial will be halted to complete an extensive safety analysis. Notification of the study enrollment halt will be sent by the Sponsor to the participating sites via telephone and email immediately after becoming aware of a safety concern. This will ensure no additional subjects are dosed until the signal has been completely evaluated. If, following safety review by the DRB and the Sponsor, it is deemed appropriate to restart dosing, a request to restart dosing with pertinent data will be submitted to the health authority.

A summary of events and assessments are provided by visit in Table 9.1.1 for Screening, Baseline and BMN 270 Infusion, in Table 9.1.2 for Post-Infusion Follow-up, and in Table 9.1.3, Table 9.1.4, and Table 9.1.5 for Safety Follow-up.

Table 9.1.6, dealing with the apeutic corticosteroid use in the event of elevated LTs, is discussed in Section 9.4.8.2.

Liver Biopsy Substudy Design

All subjects enrolled in 270-201 and who are at least one year post-BMN 270 infusion are eligible for the optional liver biopsy substudy. Subjects who consent to participate in the substudy will have a liver biopsy via either the transjugular or percutaneous (ultrasound-guided) route, according to the standard procedures of the institution. To enhance safety, all subjects will have an ultrasound examination of the liver within 3 months prior to the procedure (to ensure there are no pathological findings such as bile duct obstruction that might interfere with the safe performance of the liver biopsy) and a FibroScan of the liver within one week before the liver biopsy (to correlate with any potential histopathologic findings of fibrosis on the biopsy).

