^b Refer to Table 9.7.8.2.1 for laboratory assessments to be included, and to Table 9.7.8.3.1 for liver tests. LTs may be monitored more or less frequently (and in particular when ALT values are >1.5x ULN) based on discussion between the Medical Monitor and the Investigator and review of subject data, but LTs will be monitored at least twice weekly during periods when a subject's ALT is ≥ 3x ULN. Patients with ALT > 1.5 ULN during the study may undergo additional evaluations (eg, imaging studies including MRI or ultrasound, additional blood tests, and/or liver biopsy) at the discretion of the investigator. Additional testing of FVIII and LTs during any study week may be performed if: (1) the ALT has increased to above ULN; (2) Increases in ALT values from prior assessment are accompanied by declines in FVIII activity level; or after a discussion between the Medical Monitor and the Investigator based on a review of subject data. If FVIII levels and/or ALT values are stable over the course of several weeks, assessment of FVIII activity and ALT levels may be adjusted based on discussion between the Medical Monitor and the Investigator.

- ^c Includes hFVIII activity level (one-stage clotting assay and chromogenic substrate assay). If a subject has used FVIII within 72 hours of a measurement day, all efforts should be made to obtain FVIII activity measurements when a 72-hour interval without FVIII use is achieved; the 72-hour wash-out period is only intended for subjects who have achieved FVIII ≥ 5 IU/dL at 16 weeks after BMN 270 infusion and who have not resumed standard of care FVIII replacement therapy. If FVIII levels are elevated or stable over the course of several weeks, assessment of FVIII activity may be adjusted based on discussion between the Medical Monitor and the Investigator. A d-dimer may be considered under circumstances in which FVIII activity levels are above the normal physiological range and/or if there is a concern for a venous thromboembolism.

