^b Following initiation or completion of steroid regimen, if ALT elevation ≥ 1.5x ULN is reported, steroid management decisions will based on discussions between the Investigator and Medical Monitor. Modification of the steroid regimen may take into consideration possible confounders for the ALT elevation and impact on FVIII expression.

^c After discontinuation of corticosteroids, weekly labs for ALT and FVIII levels will be measured once a week for 4 weeks to ensure stability in values. If these assessments are already being done as part of normal study follow-up, they do not need to be duplicated.

^d Regardless of the assessments listed in the Schedule of Assessments (Table 9.1.2, Table 9.1.3, or Table 9.1.4), subjects initiated on corticosteroids will only be required to have laboratory evaluations on a weekly basis.

^e Should only be performed in subjects with a history of hepatitis B or hepatitis C prior to study entry.

270-201 Amendment 8

	Within 28 Days Before Biopsy Day	Within 7 Days Before Biopsy Day	1 Day Before Biopsy Day ^d	Biopsy Day (BD)
Informed Consent	Х			
Liver Ultrasound ^a	X			
Brief Physical Examination	X		X	Х
Hematology, Coagulation, Chemistry Assessments ^b	X		X	
Liver Tests ^b	X		X	Х
FibroScan		Х		
Local FVIII Activity Level Assessment		Х	X	Х
Pre-Biopsy Consultation ^c		Х		
Liver Biopsy ^e				Х

Table 9.1.7: Schedule of Events – Liver Biopsy Substudy

^a Liver ultrasound must be performed within 28 days prior to the scheduled biopsy, unless an ultrasound result from the prior 3 months is already available.

^b Refer to Table 9.7.8.2.1 for laboratory assessments to be included, and to Table 9.7.8.3.1 for liver tests.

^c Subjects will undergo a pre-biopsy consultation with the investigator (treating hematologist).

^d Subjects may need to repeat/extend this visit if their FVIII activity levels need adjustment before the biopsy, at the discretion of the investigator (treating hematologist).

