9.7.2 Primary Efficacy Variables

The primary efficacy measure will be the plasma FVIII activity monitored on a regular basis after BMN 270 dose. The efficacy goal of the protocol is to ascertain the dose range of BMN 270 required to convert severe HA patients to expression of FVIII at 5 IU/dL or above, (ie, a mild severity). This is associated in natural history studies with clinically superior long term outcomes (Den Ujil, 2011, Haemophilia).

The following assays (assessed by the central laboratory) will be used to measure the primary efficacy variable:

- FVIII activity (chromogenic substrate assay)
- FVIII activity by one-stage clotting assay

If a subject has used FVIII within 72 hours of a measurement day, all efforts should be made to obtain FVIII activity measurements when a 72-hour interval without FVIII use is achieved.

270-201 Amendment 8

The 72-hour wash-out period is only intended for subjects who have achieved FVIII ≥ 5 IU/dL at 16 weeks after BMN 270 infusion and who have not resumed standard of care FVIII replacement therapy.

The FVIII activity level in both assays and the number of subjects with FVIII activity ≥ 5 IU/dL in at least one of the two assays will be summarized.

FVIII activity assays will also be performed at the local laboratory at the time points indicated in Table 9.1.2, Table 9.1.3, Table 9.1.4, and Table 9.1.5 but will be used in conjunction with local lab LT assessments to monitor subject safety and need for initiation of therapeutic corticosteroid dosing; local laboratory FVIII activity assessments will not be used to assess efficacy or to measure the primary efficacy outcome of the study.

Subjects who do not respond to BMN 270 treatment (ie, treatment failure, manifesting as either failure to achieve FVIII activity ≥ 5 IU/dL by Week 52 or inability to maintain independence from prophylactic FVIII replacement therapy due to joint bleeding episodes, in the judgment of the Investigator) may, at the Investigator's discretion and after discussion with the Medical Monitor, follow an abbreviated visit schedule after Week 52, as applicable and at the discretion of the Investigator.

Timing of assessment by these assays is provided in Table 9.1.2, Table 9.1.3, Table 9.1.4, and Table 9.1.5. Details on performing the assays are included in the Laboratory Manual.

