^f Blood samples will be collected to evaluate biochemical, molecular, cellular, and genetic/genomic aspects relevant to hemophilia A, coagulation, and/or AAV gene transfer, and to develop assays used for these evaluations. Subjects may choose to opt out of the exploratory genetic/genomic research being done to study or try to discover genes that are not yet known to be associated with hemophilia A. While exploratory samples will be collected at the time points indicated above, testing of these samples will be performed only as deemed necessary by the Sponsor.

BOMARIN	270-201 – Amendment 6	Page 40
---------	-----------------------	---------

Table 9.1.4: Schedule of Events – Safety Follow-Up

					Ye	ear 1 -	- Weel	KS *					Years 2-5*	Year 2*	Years 3-5*	ETV
Assessment	33	34	35	36	38	40	42	44	46	48	50	52	Q3M	Q4W	Q6W	
Physical examination ^a	Х	Х	Х	Х	Х	Х	Х	Х	Х	Х	Х	Х		Х	Х	Х
Weight ^a												Х	Xa			
Assessment of Adverse Events and Concomitant Medications (including review of subject diary for bleeding and FVIII use)	Х	X	Х	Х	Х	Х	X	X	X	Х	Х	X		X	Х	Х
Vital Signs	Х	Х	Х	Х	Х	Х	Х	Х	Х	Х	Х	Х		Х	Х	Х
Blood chemistry, haematology, coagulation screen, and $CRP^{\rm b}$				Х		Х		Х		Х		X	Х			Х
Urine Tests ^b				Х		Х		Х		Х		Х	Х			Х
Liver Function Tests (local) ^b	Х	Х	Х	Х	Х	Х	Х	Х	Х	Х	Х	Х		Х	Х	Х
FVIII assays (local) ^c	Х	Х	Х	Х	Х	Х	Х	Х	Х	Х	Х	Х		Х	Х	Х
Liver Function Tests (central) ^b	Х	Х	Х	Х	Х	Х	Х	Х	Х	Х	Х	Х		Х	Х	Х
FVIII assays (central) ^d	Х	Х	Х	Х	Х	Х	Х	Х	Х	Х	Х	Х		Х	Х	Х
AAV5 antibody titer				Х		Х		Х		Х		Х	Х			Х
FVIII antibody titer				Х				Х				Х	Х			X
PBMC Collection (for determination of FVIII and Capsid specific CTL activity)		Х		Х				Х				Х	Х			Х
Von Willebrand Factor Antigen (VWF:Ag)				Х		Х		Х		Х		Х	Х			Х
Direct Thrombin Test					Х							Х	Х			Х
PCR of vector DNA in blood, saliva, urine, semen, and stools ^e				Х		Х		Х		Х		Х	Xe			X
Exploratory biomarker assessments ^g				Х		Х		Х		Х		Х		Х	Х	Х
Haemo-QoL-A QoL assessment												Х	Xf			Х

Proprietary and Confidential

BIOMARIN	270-201 – Amendment 6	Page 41
----------	-----------------------	---------

* Visit windows are ± 48 hours through Week 36, then ±1 week until Week 52 and ± 2 weeks for visits in Years 2-5. For LFT, FVIII, and exploratory biomarker testing during Years 2-5, the visit windows are every 4 weeks (+ 2 weeks) during Year 2, and every 6 weeks (±2 weeks) during Years 3-5.

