 Schedule of Events – Therapeutic Corticosteroids

	Steroid Treatment Period ^d											Post-Steroid Period ^c				
	Week 1	Week 2	Week 3	Week 4	Week 5	Week 6	Week 7	Week 8	Week 9	Week 10	Week 11 ^b	Week 1	Week 2	Week 3	Week 4	Week 13
Therapeutic corticosteroids (dose in mg/day) ^a	60 mg	60 mg	40 mg	40 mg	30 mg	30 mg	20 mg	20 mg	15 mg	10 mg	5 mg					
FVIII activity testing												Х	Х	Х	Х	
Liver function testing												Х	Х	Х	Х	
Hepatitis B testing ^e						Х						Х				X
HCV Viral Load ^e						Х						Х				X

^a Therapeutic corticosteroids may be initiated when a subject's ALT value is ≥ 1.5x ULN or based on review of FVIII and liver enzyme data after consultation between the Investigator and the Medical Monitor.

^b Following initiation or completion of steroid regimen, if ALT elevation ≥ 1.5x ULN is reported, steroid management decisions will based on discussions between the Investigator and Medical Monitor. Modification of the steroid regimen may take into consideration possible confounders for the ALT elevation and impact on FVIII expression.

^c After discontinuation of corticosteroids, weekly labs for ALT and FVIII levels will be measured once a week for 4 weeks to ensure stability in values. If these assessments are already being done as part of normal study follow-up, they do not need to be duplicated.

^d Regardless of the assessments listed in the Schedule of Assessments (Table 9.1.2, Table 9.1.3, or Table 9.1.4), subjects initiated on corticosteroids will only be required to have laboratory evaluations on a weekly basis.

^e Should only be performed in subjects with a history of hepatitis B or hepatitis C prior to study entry.

BOMARIN	270-201 – Amendment 6	Page 43
---------	-----------------------	---------

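### Table 9.1.6 footnote d, the weekly-lab rule during a steroid course, as worded overrides the mandatory twice-weekly liver tests at ALT ≥3x ULN, and its list of tables stops at Week 52

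*Protocol*

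**What the plan says.** In Amendment 8, the current version, Table 9.1.6 (Section 9.1) lays out an 11-week prednisolone taper. Its grid marks no liver or FVIII test in the 11 steroid weeks; those marks begin in the post-steroid period. Frequency during the course is left to footnote d, which opens "Regardless of the assessments listed in the Schedule of Assessments (Table 9.1.2, Table 9.1.3, or Table 9.1.4" and rules that "Table 9.1.2, Table 9.1.3, or Table 9.1.4), subjects initiated on corticosteroids will only be required to have laboratory evaluations on a weekly basis".

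The provisions it has to fit with are these:

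- Footnote b of Tables 9.1.2, 9.1.3 and 9.1.4 lets LT frequency be adjusted, "but LTs will be monitored at least twice weekly during periods when" ALT is ≥3x ULN. Table 9.1.5 carries the same footnote.
- Table 9.1.4 now ends at Week 52. Years 2-5 are in Table 9.1.5: every 4 weeks in Year 2, every 6 weeks in Years 3-5, or only the 12-weekly and End of Year visits for treatment failures on the optional abbreviated schedule.
- Section 9.4.8.2, on steroid treatment, spans both the Post-Infusion and the Safety Follow-Up periods. Section 9.7.2 says that local FVIII tests at time points up to and including Table "9.1.5 but will be used in conjunction with local lab LT assessments to monitor subject safety and need for initiation of therapeutic corticosteroid dosing". Courses begun in Years 2-5 are therefore foreseen.
- On managing the course, Table 9.1.6 footnote b says: "Modification of the steroid regimen may take into consideration possible confounders for the ALT elevation and impact on FVIII expression". After the course, footnote c says "weekly labs for ALT and FVIII levels will be measured once a week for 4 weeks", with no list of tables attached.

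**The concern.** Footnote d is an operative safety rule, and a site can misread it in two ways.

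The first concerns the most worrying range of ALT. Steroids may start at ALT ≥1.5x ULN, so a subject at ≥3x ULN is likely to be on them. That subject is told by one footnote to have LTs at least twice a week, and by another that, whatever the first table says, only weekly laboratory work is required.

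The second concerns time. If the list of tables is taken as the scope of the rule, a course begun after Week 52 with ALT below 3x ULN has no weekly minimum. The taper would then be managed on ALT and FVIII results that nothing obliges the site to obtain weekly, although four weekly tests are required once the drug is stopped.

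**Working it through.** **Course length.** The taper steps in Section 9.4.8.2.1 are 2+2+2+2+1+1+1 = 11 weeks, which reproduces the stated total.

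**Defect 1: weekly against twice weekly.** If ALT stayed ≥3x ULN for the whole course, footnote d requires 11 × 1 = 11 LTs and footnote b at least 11 × 2 = 22. More generally, each week on steroids at ≥3x ULN loses at least one LT if footnote d prevails.

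**Defect 2: required tests after Week 52 if the list confines the rule to Year 1.** The nominal calendar from Table 9.1.5 and Section 12.8 is:

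- Year 2: Weeks 56, 60, …, 104.
- Years 3-5: every 6 weeks, restarting after Weeks 104, 156 and 208, plus the End of Year visits (110, 116, …, 152, 156, 162, …, 260).
- Abbreviated: Weeks 64, 76, 88, 104, then the same pattern to Week 260.

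Take a course starting at a visit in Week t. Count the visits v with t < v ≤ t + 11, keeping only courses that finish by Week 260. Examples:

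- t = 52: Weeks 56 and 60, so 2.
- t = 104: Week 110 only, so 1.
- t = 146: Weeks 152 and 156, so 2.
- Abbreviated, t = 64: the next visit is Week 76, 12 weeks away, so 0.

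| Trigger visits | Nominal dates | With visit windows | Weekly rule |
|---|---|---|---|
| Weeks 52-100, full schedule (13) | 2 at all 13 | 1-3 | 11 |
| Weeks 104-244, full schedule (25) | 1 at 21; 2 at Weeks 146, 152, 198 and 204 | 1-2 | 11 |
| Abbreviated schedule (16) | 0 at all 16 | 0-1 | 11 |

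The windows are ±2 weeks in Years 2-5 (±1 week for the Week 52 visit). The counts leave out the triggering test and the four post-steroid tests. They apply while ALT is below 3x ULN; above that, Table 9.1.5 footnote b itself requires twice-weekly LTs, though not FVIII.

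**How the wording arose.** In Amendment 6, Table 9.1.4 also held the later years; its own footnote says "For LFT, FVIII, and exploratory biomarker testing during Years 2-5, the visit windows are every 4 weeks". The same list of tables therefore reached Years 2-5. Footnote b then contained no twice-weekly rule. Amendment 7 moved Years 2-5 into Table 9.1.5, added the twice-weekly rule, and left footnote d as it was. Amendment 8 extended six other cross-references to the new table (Sections 9.1, 9.7.2 twice, 9.7.5, 9.7.6 and 9.7.8.1); Section 9.1 now reads "in Table 9.1.3, Table 9.1.4, and Table 9.1.5 for Safety Follow-up". It did not extend footnote d.

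**The case against.** A reader might infer that the protocol cuts monitoring after Week 52 to one or two tests, or none, per course. The documents do not support that. The list in footnote d identifies the schedules being set aside, not the subjects covered. The operative clause has no time limit, and the footnote hangs on the whole steroid treatment period. The Amendment 6 wording covered Years 2-5. Section 9.7.4 was also left at Tables 9.1.2-9.1.4, which points to incomplete editing rather than a changed rule.

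Nor is footnote d the only source of weekly labs in every course: through Week 36 the schedule tables already require weekly LTs and FVIII. It carries the weekly requirement only for later courses.

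There are also safeguards. ALT ≥1.5x ULN goes to the medical monitor within 30 minutes (Section 9.4.8.2.1) and is an event of special interest reportable within 24 hours (Section 10.2.1). Clinically significant results are to be repeated at the Investigator's discretion (Section 9.7.8.2), and unresolved adverse events followed to resolution or stability (Section 10.6). Eleven unmonitored weeks are not a realistic outcome.

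On the first defect, the Amendment 7 summary says that twice-weekly testing was meant to be mandatory, so the intended precedence is clear.

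What remains is narrower. The safeguards act once a sample has been drawn, or depend on discretion. None sets a weekly minimum after Week 52 at ALT from 1.5x to below 3x ULN, and none sets one for FVIII. A site should not need the amendment history to know which footnote governs.

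**Conclusion.** Footnote d needs correcting, at minor-to-moderate severity. The conflict with the twice-weekly rule is there on the face of the text: 11 LTs against at least 22 in the limiting case of ALT ≥3x ULN throughout. The missing Table 9.1.5 is a stale cross-reference that leaves the rule ambiguous after Week 52. Weekly testing is the more natural reading, and the figures of 1-2 (1-3 with windows, 0-1 abbreviated) against 11 hold only under the other one.

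The comparison with 11 also assumes that the footnote's laboratory evaluations mean ALT and FVIII, which footnote c names but footnote d does not, and that its *only* was meant to set a weekly frequency rather than merely a ceiling.

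The practical reach is small. Enrolment is capped at 15, Section 7.4 reports that for most subjects the ALT rise was only slightly above ULN, and the number of courses begun after Week 52 is not given. The Week 16 endpoint is not affected.

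**What to change.** Replace footnote d with a sentence to this effect: *Whatever Tables 9.1.2, 9.1.3, 9.1.4 or 9.1.5 schedule, the abbreviated schedule included, a subject on corticosteroids has ALT and FVIII tested at least once a week; the minimum of two LTs a week while ALT is ≥3x ULN continues to apply.*

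Both halves are needed. Adding Table 9.1.5 alone would extend the apparent override of the twice-weekly rule to Years 2-5. Section 9.4.8.2 needs no change, since routine Years 2-5 frequencies are already fixed in Table 9.1.5 and Section 12.8.

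The cost is one sentence and, for each course begun after Week 52, about 11 − 3 = 8 to 11 − 0 = 11 extra local draws, in at most 15 subjects. There are none where sites already test weekly.
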